13.3.3. Secondary outcome analysis

A range of exploratory secondary analyses will be undertaken including but not limited to those specified below with the full analysis being specified in the statistical analysis plan.

8 Weekly Micro Assessments

In addition to the endpoints at 16 and 52 weeks the study also includes multiple weekly micro assessments in order to assess change in hypothesized mechanisms-of-change over time during the course of therapy (recognising that change often happens in first half of therapy), and thereby, test if (a) manipulated treatment components influence hypothesized mechanisms and/or alternative mechanisms (e.g. does presence of Be Kind increase self-compassion more than absence); (b) track any such change over time; (c) enable a test of mediation across multiple time points and with prospective analysis of whether any changes in process measures predicts change in RNT and mediates the effect of factors on change in RNT.

The micro-assessments will be analysed using a repeated measures analysis of variance to assess change in hypothesized mechanisms-of-change over time during the course of therapy as specified prior.

Analysis of PWP/coach effect

The study is supported by a relatively small number of PWPs (UK) and coaches (US). With the initial number employed expected to be fewer than 10. All PWPs and coaches will also be expected to deliver all intervention arms and the PWP/coach will be selected for the participant prior to randomisation. All steps will be taken to minimise the PWP/coach effect and to ensure that it is balanced across treatment conditions. However, as part of our secondary analysis we will still investigate the PWP/coach effect and its potential for impacting on the outcome.

52 Week follow-up analysis

Where possible we will obtain long-term follow-up (52 weeks) on all participants. Analysis will be analogous to the primary analysis using an adjusted multilevel mixed model to investigate the effect of the four treatment factors and their first order interactions.

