8.1.2. Payment

Participants will be offered an online shopping voucher for the value of £30 for completion of each of the activities listed below.

- Completion of baseline data AND a minimum of 60% of the baseline EMA
- Completion of 6 or more of the micro-assessments during the intervention period
- Completion of the 16-week post-randomisation data AND a minimum of 60% of the follow-up EMA
- Completion of the 52-week post-randomisation data
- Participation in a 16-week post-randomisation qualitative interview (a selected subset of overall sample)
- Participation in a 52-week post-randomisation qualitative interview (a selected subset of overall sample)

Vouchers for participants in the UK will be monitored and administered by the University of Exeter.

USA-specific detail

Participants will be offered online shopping vouchers up to a total of \$200 for the completion of the above listed activities (excluding the qualitative interviews which will not be conducted in the USA). Payments to participants in the USA will be monitored and administered by the trial management team at UCLA.

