8.5. Follow up data collection

8.5.1. Weekly micro-assessments (during the intervention stage)

At week 1, 2, 3, 4, 5, 7, 9, 11, 13, 15, participants will receive prompts to complete brief questionnaires (micro-assessments) via the mPath App. The schedule for these questionnaires will start from the day the participant reinstalls mPath with their second invitation code, provided to them at the point of randomisation. The questionnaires collected during the micro-assessments will include condensed (2-3 item versions) of self-report and brief problem description measures of mediators, as well as brief outcome measures of RNT, anxiety (GAD2), depression (PHQ2), as detailed in Table 3. Participants will also be prompted to complete two brief questions in weeks that the full micro-assessment is not required (weeks 6, 8, 10, 12 and 14). This is to maintain engagement and to keep m-Path live on their phones (i.e., prevent the App from being put to sleep by the operating system).

Participants will have a +4 day window each week to complete the micro-assessments, after which the assessment will no longer be accessible to the participant. If any of the micro-assessments or engagement prompts are not completed, the participant will be sent an email to increase their engagement with the app and reminding them to open the m-Path app to ensure future survey notifications are received (i.e. to avoid the app going into sleep mode).

During the intervention period we will also collect data on engagement with the intervention (see Section 9 for more details).

8.5.2. 16 weeks post-randomisation

At 16-weeks post randomisation, participants will receive an automated SMS text message and an email with a link to complete the follow up questionnaires as surveys via REDCap Academic. On week 16 participants will also be invited to complete EMA for another 10-14 days (see the EMA thresholds under the Baseline Section 8.3) via the m-Path App. The schedule for the EMA will start from the day the participant reinstalls mPath with their second invitation code, provided to them at the point of randomisation. The questionnaires and data collected at 16 weeks post-randomisation are detailed in Table 3.

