13. STATISTICS AND DATA ANALYSIS

13.1. Target sample size and justification

To detect a Minimum Clinically Important Difference of Standardized Mean Difference (SMD) (Cohen's d) = 0.20 (i.e., a small effect size below which any effect is unlikely to be an important mechanism or specific ingredient) with 90% power at $\alpha=0.05$ in main effect of treatment component(s) requires N=1054 (n=527 per level of each factor). Conservatively estimating 52% dropout attrition posttreatment, we require N≈2192 for Analysis of Variance (or equivalent) to test main effects and two-way interactions. Recruitment rates from our prior online trials confirm this target is feasible.

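### Repeated-measures ANOVA, read classically, would limit the within-treatment mechanism analysis to people who complete all ten micro-assessments, although the protocol expects incomplete series

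*Protocol*

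**What the plan says.** Section 13.3.3 names the method for the micro-assessments: "The micro-assessments will be analysed using a repeated measures analysis of variance". No handling of missing occasions is attached to that sentence. The block carries the heading "8 Weekly Micro Assessments".

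Section 8.5.1 gives ten occasions, not eight, and they are not all weekly: "At week 1, 2, 3, 4, 5, 7, 9, 11, 13, 15, participants will receive prompts". Each stays open for four days, "after which the assessment will no longer be accessible to the participant". Section 8.1.2 pays a voucher for "Completion of 6 or more of the micro-assessments during the intervention period". Section 13.1 plans for heavy loss: "Conservatively estimating 52% dropout attrition posttreatment, we require N≈2192".

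Elsewhere the method is different. Section 13.3 plans multilevel mixed models with a PWP/coach random effect under a treatment-policy estimand, and sections 13.3.2 and 13.3.3 use mixed models at 16 and 52 weeks. Section 13.5 bases the primary analysis on all randomised participants. The table in section 3.3.5 lists the micro-assessments among the mechanism measures for the primary objective.

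**The concern.** Classical repeated-measures ANOVA drops a person's whole series if one occasion is missing. A participant who meets the protocol's own payment threshold with six to nine assessments would contribute nothing.

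Three things are at stake.

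- **Selection.** Completing all ten occasions is behaviour after randomisation that the components may themselves affect. Comparing high and low levels among completers is no longer the randomised comparison.
- **Loss of early data.** Section 13.3.3 notes that change tends to come early in therapy. Complete-case analysis discards the early records of everyone who stops later.
- **Precision.** The loss could be large, depending on how occasions are missed.

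The micro-assessments are the only repeated measure of mechanisms during treatment, and section 3.3.3 relies on them for temporal precedence in the mediation analysis.

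**Working it through.** **Inputs from the protocol.** 2,192 randomised; 52% attrition post-treatment, so 48% retained at week 16; ten occasions at weeks 1, 2, 3, 4, 5, 7, 9, 11, 13 and 15; SMD 0.20, alpha 0.05, 90% power (section 13.1).

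**Assumptions, not in the protocol.** Dropout accrues at a constant hazard over 16 weeks. Completion per occasion while retained is 80% to 95%. Misses are independent, or clustered within people as shown below.

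**The plan's own figure.** A two-sided two-sample t calculation at SMD 0.20 and 90% power gives 527 per level, so 1,054, as stated. The normal approximation gives 526 per level, so 1,052. Inflating: 1,054 / 0.48 = 2,196 and 1,052 / 0.48 = 2,192. The plan's total is reproduced to within rounding. It gives no figure for the micro-assessment analysis.

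**Planned dropout alone.** Share still present at week 15 = 0.48^(15/16) = 0.5025. Complete series = 0.5025 × 2,192 ≈ 1,102.

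**Dropout plus independent misses.** Share complete = 0.5025 × p^10. Power for a single-occasion main effect uses z = 0.20 × √N / 2 − 1.96.

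| Completion while retained (p) | p^10 | Share complete | N | Power at SMD 0.20 |
|---|---|---|---|---|
| 100% | 1 | 50% | 1,102 | 91% |
| 95% | 0.599 | 30% | 660 | 73% |
| 90% | 0.349 | 18% | 384 | 50% |
| 80% | 0.107 | 5% | 118 | 19% |

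**Clustered misses, no separate dropout.** Beta-binomial with mean completion μ and within-person correlation ρ: P(all ten) = B(a+10, b) / B(a, b), where a = μ(1/ρ − 1) and b = (1 − μ)(1/ρ − 1).

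| Mean completion | Independent | ρ from 0.1 to 0.5 |
|---|---|---|
| 90% | 35% (764) | 48% to 74% (1,060 to 1,622) |
| 80% | 11% (235) | 22% to 54% (482 to 1,179) |
| 70% | 3% (62) | 9% to 38% (204 to 838) |
| 60% | 0.6% (13) | 4% to 26% (79 to 579) |

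**Records discarded under dropout alone.** Expected numbers at the ten occasions are 2,094, 2,000, 1,910, 1,825, 1,743, 1,590, 1,451, 1,323, 1,207 and 1,102. They sum to 16,245 of 21,920 planned records (74%). A complete-case ANOVA uses 10 × 1,102 = 11,020 (50%). It discards 16,245 − 11,020 = 5,225 records. Of these, 9,572 − 5 × 1,102 = 4,062 (78%) come from weeks 1 to 5. A likelihood-based mixed model keeps all 16,245.

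**The case against.** The strongest reply has five parts.

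- **Exploratory status.** Section 13.3.3 introduces these analyses as exploratory and leaves full detail to the SAP. This bears on weight. It does not remove the point, because the protocol names a method and the SAP would have to depart from it.
- **Loose wording.** Section 13.1 sizes the trial for analysis of variance or an equivalent, while section 13.3 specifies mixed models for the same effects. ANOVA may therefore be loose wording here too. If so, the text should say what is meant; the classical reading is the natural one.
- **Imputation.** Sections 13.3 and 13.6 plan it. But section 13.3 makes it conditional on need and Trial Steering Committee agreement, section 13.6 presents the results alongside the main analysis, and section 13.6 covers outcomes and explanatory variables. Section 3.3.3 classes micro-assessments as process measures, so the cover is unclear.
- **Restriction elsewhere.** Sections 13.3.2 and 13.3.5 say that all analysis includes participants with 16-week primary outcome data. Applied here, that would already remove about half the sample. This is a further reason to define the analysed set for the micro-assessments, not a defence of complete cases.
- **Size.** The 52% is described as conservative, reminder emails follow missed assessments, and everyone randomised has already completed at least 36 prompts on the same app. The voucher threshold is a payment rule, not a forecast. Power for a factor effect averaged over ten occasions also exceeds the single-occasion figure: with 384 people and an assumed within-person correlation of 0.4 to 0.7, it is about 82% to 63%. All of this stands.

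A reader might also infer that standard errors would be invalid for want of sphericity, or that the PWP/coach effect is ignored. Sphericity concerns the time and factor-by-time tests, not the between-person main effects, and standard corrections exist. Section 13.3.3 plans a separate PWP/coach analysis. Both are minor.

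**Conclusion.** The point holds for the within-treatment mechanism analysis. As worded, the method conflicts with what the protocol expects of the data and with its own treatment-policy, all-randomised approach. If planned attrition accrues evenly, about half of those randomised are lost before any intermittent miss is counted. The remaining 1,102 would still give about 91% power at SMD 0.20, so in that case the main damage is selection and the loss of early records. With intermittent misses the number falls further, but how far depends on a completion rate and a degree of clustering that the protocol does not give.

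A reader might infer that the whole mechanism question in the primary objective would rest on a small subset, or that 384 people and 50% power is the expected result. The documents support neither. Mechanisms are also measured by questionnaires at baseline and 16 weeks and by EMA, and the 384 is one scenario within a wide range.

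The count of 8 in the heading contradicts the ten scheduled occasions under any reading.

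**What to change.** Replace the ANOVA sentence in section 13.3.3 with a linear mixed model for repeated measures that:

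- uses all available occasions from every randomised participant, and says that it is not limited to those with 16-week primary outcome data;
- includes the four factors and their two-way interactions, each by time;
- adjusts for the baseline value of the mediator where collected, and for the stratification variables;
- includes the PWP/coach effect and a suitable within-person covariance;
- states its missing-at-random assumption.

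Correct the heading to the ten scheduled occasions, and do not call them weekly.

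The cost is one paragraph of protocol wording, carried into the SAP. No new data, visits or participants are needed, and standard software fits the model.

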13.3.4. Subgroup analyses

Primary and secondary analyses will be extended to explore potential subgroup effects by including additional interaction terms between the factor allocation. The study is powered to detect overall difference between the factors with the inclusions of the first order interactions and therefore insufficiently powered to definitively investigate subgroup analysis. The results may, however, be of exploratory value. Results will be presented using confidence intervals, as well as a global p value for the interaction between the treatment factor and each of our identified sub-groups (adjusted for the first order treatment factor interactions) and they will be interpreted with due caution. Our identified subgroups are:

1. Country (UK, USA)
2. Caseness (as defined by standard thresholds on GAD-7 for anxiety and PHQ-9 for depression)

13.3.5. Adjusted analysis

All analysis will be based on a treatment policy estimand and will include participants with primary outcome data at 16 weeks, we will adjust for the stratification variables (location (UK or USA), caseness or not for anxiety or depression) and if necessary adjust for any significant imbalance in baseline participant characteristics (if there is $>1SD$ difference in mean or >10 percentage points for categorical data and the variable is thought to be predictive of outcome).

13.3.6. Sensitivity analysis

All of the analyses will be presented with appropriate confidence intervals for their parameters and estimates. The inclusions of further sensitivity analyses will be dependent on the assumptions made in

the models (e.g. the need for data imputation, inclusion of additional interaction terms) and will be undertaken following agreement from the Trial Steering Committee and where appropriate specified in the statistical analysis plan.

13.4. Interim analysis and criteria for the premature termination of the study

There is no planned interim analysis or criteria for the premature termination of the study based on efficacy. However, the DMEC will receive regular and timely information related to study safety and are at liberty to request analysis of interim data including reporting any concerns to the TSC regarding the continuation of the study.

13.5. Participant analysis population(s)

Analysis will be undertaken on three participant populations:

- **All-randomised population:** Any participant randomised into the study, regardless of whether they received study treatment (intention-to-treat)
- **All-treated population:** Any participant randomised into the study that received any amount of study treatment
- **Protocol-compliant population:** Any participant who was randomised and received the protocol required treatment exposure and required protocol processing

With the primary analysis based on a treatment policy estimand and therefore based on the all-randomised population. The results of the analysis on the all-treatment and protocol compliant populations will be used to provide insight related to the primary analysis.

13.6. Procedure(s) to account for missing or spurious data

The data will be collected and stored to both highlight and minimise the chances of missing or spurious data. Patterns of missing outcome data at follow-up will be extensively investigated. Imputation models will be used to impute missing primary and secondary outcome data and any explanatory variables at all follow-up time points. Results for the between group comparisons based on these imputed data sets will be presented in addition to the primary analysis described. Propensity for missingness and potentially spurious values associated with baseline characteristics will be investigated; imputation models will include treatment allocation as well as stratification variables, baseline variables, and any variables associated with missingness or included in the models as covariates due to baseline imbalance. The potential for introducing bias through the imputation of missing data will be extensively considered and where appropriate highlighted.

13.7. Other statistical considerations.

No formal p-value adjustment will be made for multiple testing; the results of the treatment policy estimand analyses will be interpreted first, and the results of the additional analyses interpreted in this light. The focus of the analysis will be on the four treatment factor comparisons. However, the first order interactions will also be investigated and reported on. Interpretation of results will draw focus on confidence intervals rather than emphasising p-values.

Given the complexity of the study the lead statistician will be unblinded following the sign-off of the statistical analysis plan. However, the primary analyses will be performed by a statistician who remains blinded to group allocation and will be presented as such to the investigators. The results will be discussed and interpreted prior to the unblinding of group allocations. Additional analyses will then be performed following unmasking.

14. DATA MANAGEMENT

Data management activities are summarised in this section. Detailed data management activities are described in a separate Data Management Plan (DMP).

14.1. Data collection tools and source document identification

Study data will primarily be collected online. The source data will be the eCRFs held in REDCap Academic, the MyDataHelps platform, and the mPath app. All data will be provided directly by the participant with the following exceptions:

- Data reported by a participant over the telephone that is entered into the eCRF by the research team (e.g. in the case that a participant does not complete the questionnaires and receives a reminder phone call from the research team, and the participant opts to complete the questionnaires over the phone).
- SAE report eCRFs will be completed by the PWP (UK)/coaches (USA)/site leads
- Change of participation status eCRFs will be completed by the research team.
- The participant contact log/appointment log will be completed by the research team/PWP (UK)/coaches (USA).

A full audit trail will be maintained on REDCap Academic, including the date and time data was first recorded, by whom if the user is a staff user (i.e., not a participant) and a full history of amendments made to the original data. Any data that would ordinarily be participant-reported that was entered into the eCRF by a PWP/coach/researcher will be specified so that the source is clearly distinguishable. For the data entered into the m-Path app an audit trail will be automatically logged of the time that each survey or reminder is sent, received, accessed and completed. The entered data cannot be edited by staff or participants on m-Path once it has been submitted.

This is a decentralised trial, with research sites defined at the country level. Each participating country will hold and be in control of their respective data.

PWP/coaches will maintain risk logs separate to the REDCap database, but this will not be included as 'research data'.

Data collected as part of qualitative interviews with participants will be audio-recorded via Teams or Zoom, or using an encrypted GDPR-compliant audio-recording device. Audio-recordings will be the source of the interview-generated data and will be stored until interview analysis is complete. Audio-recordings will be transcribed into Word documents by a third-party transcription service.

USA-specific detail

Only USA-based participants and coaches/members of the research team based at UCLA will be able to enter data into the USA instance of REDCap Academic. Researchers/PWP at the lead site in the UK will not have access to the USA instance of REDCap Academic.

14.2. Data handling and record keeping

A full data management plan (DMP) will be implemented for the study. The DMP can be viewed upon request to the Sponsor (Research Ethics, Governance & Compliance Office, University of Exeter). An

international data sharing agreement will be in place for the study to facilitate the sharing of data between University of Exeter (UK), UCLA (USA) and LMU (Germany).

EMA and micro-assessment data from m-Path will be transferred to ExeCTU at least 6-monthly and stored securely on a SharePoint site with restricted access. LMU will report completion data to ExeCTU at least monthly to facilitate the sending of reminders, production of oversight reports and payment of participants for completion of activities.

The research team at UCLA will provide regular (approximately monthly) pseudonymised exports of both completion data from MyDataHelps and data from their instance of REDCap to the research team at ExeCTU for the purpose of reporting to oversight committees. These exports will not contain any personal identifiable data and will be transferred to ExeCTU via a SharePoint site, managed by ExeCTU, with access restricted to the study team.

14.3. Access to Data

Participants will be granted access to enter their data using REDCap surveys. They will not have user access to REDCap and will not be able to log in to view, amend or delete previously submitted data. Participants will be able to view and delete their previously submitted data collected via the m-Path app, but will not be able to amend data in m-Path once submitted. Participants will set up a user account on MyDataHelps which they will be able to access for the duration of their intervention period.

User access to REDCap will be restricted to staff members working on the study with a genuine business need. User permissions will be set as appropriate for the individuals role on the study. 'Read Only' access will be granted to representatives of the Sponsor research governance team and regulatory bodies upon request for audit and inspection purposes, in line with participant consent.

LMU will have access to the pseudonymised data collected in mPath. Secure transfer of data from mPath to ExeCTU for the purposes of study monitoring and reporting will be made at least 6-monthly.

Participants personal email address will be communicated to MyDataHelps which is managed by UCLA and hosted on a server in the USA. This is for the purpose of setting up their user account to access the intervention. During account set up on MyDataHelps participants will be given the option to volunteer their name and phone number for the purpose of receiving personalised messages from the platform directly related to their completing the intervention.

PWPs/coaches may have 'read-only' accounts on m-Path and MyDataHelps to view completion data for their respective participants (UK/USA) if required for appointments.

Qualitative research data collected as part of the interviews for the process evaluation will be stored on a restricted SharePoint site hosted by the University of Exeter, with access granted to authorised members of the research team who need to collect, review or analyse the qualitative data. This will include the original audio-recordings and the pseudonymised transcribed documents. Access to the pseudonymised transcribed documents and pseudonymised quantitative data will be provided to the lead process evaluation researcher at the University of Southampton.

The SMS text messaging service provider will receive the participant's telephone number and the wording for the follow-up and reminder text messages. Their text messaging data centre is located in the United States. Participants do not have to respond to any text messages so no data will be sent

back via the SMS service provider. No other identifiable information will be shared with the SMS service provider. By linking directly into REDCap, REDCap will be used to store logs and records of communications with participants and the SMS service provider will delete their logs and not hold data after it has been fed back into REDCap.

USA-specific detail

In the USA, to enable day-to-day management and monitoring of the study, members of the research team at UCLA (coaches) and members of the study team responsible for coordinating the study locally will have access to the US REDCap instance, with permissions set as appropriate for their role. The local lead investigator will have data entry access to SAE report forms. Access will not be granted to the Sponsor for audit and inspection due to institutional limitations on external accesses, however, pseudonymised data exports will be regularly transferred to ExeCTU and can be monitored by the Sponsor if required.

LMU will notify the research team at UCLA of completion status for participants in relation to EMA and the weekly micro-assessments to facilitate the sending of reminders and voucher payments for those participants. This summary data will be transferred to UCLA via a SharePoint site, managed by ExeCTU, with access restricted to the study team.

